1.8 Brief description of proposed analysis

Efficacy analysis population: We will use the intention-to-treat (ITT) population which includes all randomised participants analysed in the treatment arm to which they were allocated to regardless of treatment subsequently received, multiple imputation will be used to account for any missing data such that all randomised participants are included in the final analysis. At the formal interim analysis multiple imputation will be undertaken if greater than 5% of outcome data are missing, if \leq 5% missing a complete case analysis will be undertaken.

Safety analysis population: We will include participants who received at least one dose of study medication and analysis will be according to treatment received, regardless of randomised treatment assignment.

The formal interim analysis will be conducted after 171 participants have been recruited and have completed 14 days of follow-up after randomisation. If an experimental treatment is recommended to continue an additional 95 participants will be recruited for each arm that continues and final analysis will be completed after all participants have completed 28 days of follow-up after randomisation.

Formal interim and final analyses will be carried out sub-group blind and follow the ITT principle. That is, all randomised patients will be analysed in the treatment arm to which they were allocated to regardless of treatment subsequently received, multiple imputation will be used to include all randomise participants for the final analysis, at the formal interim analysis multiple imputation will be undertaken if greater than 5% of outcome data are missing. The analysis of the serious adverse events will be undertaken on the safety population.

All regression analysis will include adjustment for age group (<65 years or ≥65 years) and site where appropriate, since these were stratification factors in the randomisation.

All confidence intervals will be presented at the 95% level.

For the formal interim analysis (stage 1) one-sided p-values \leq 0.25 will indicate that an experimental treatment should be recommended to continue to stage 2 and for the final (stage 2) analysis one-sided p-value \leq 0.027 will be interpreted as statistically significant for the primary outcome.

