2.4 Standard of Care

Please see section 2.4 in SAP I. This will be undertaken for stage I and stage II

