3.1 Primary outcome of the main study - Modified WHO grading

3.1.1 Definition of the primary outcome

The proportion of participants progressing from mild to severe COVID-19 pneumonia within 14 days. Where severe COVID-19 pneumonia is defined by a modified WHO COVID-19 Ordinal Score ≥ 5 (on the 9 point scale), comprising the following indicators of disease severity: Death (9) OR Requirement for invasive ventilation plus organ support (8) Requirement for invasive ventilation (7) OR Requirement for non-invasive ventilation including CPAP or high flow oxygen (6) OR O₂ saturation < 90% on \geq 60% inspired oxygen (5). These are captured in the database as follows:

Modified WHO COVID-19 Ordinal Score	Database
(9) Death	
(8) Requirement for invasive ventilation plus organ support	Has the patient required renal replacement therapy? OR Has the patient required ECMO? OR Has the patient required inotropic support? AND Has the patient required intubation and mechanical ventilation?
(7) Requirement for invasive ventilation	Has the patient required intubation and mechanical ventilation?
(6) Requirement for non-invasive ventilation including CPAP or high flow oxygen	Has the patient required NIV, CPAP or high flow nasal oxygen?
(5) O ₂ saturation < 90% on ≥60% inspired oxygen	Has the patient's oxygen saturation been < 90% on 60% inspired oxygen?

3.1.2 Statistical model at stage 1

The stage one primary analysis will consist of fitting two separate binomial regression models for the RUX vs SOC and FOS vs SOC comparisons in order that we can undertake an adjusted analysis using a propensity score approach. Specifically a generalized linear model with WHO COVID-19 status (<5 or ≥ 5) as the outcome and treatment group as a covariate. We will adjust the treatment effect for the

following prespecified covariates using a propensity score approach. The propensity score model will include:

- baseline WHO COVID-19 score (3 or 4)
- age ($<65 \text{ or } \ge 65$)
- receipt of dexamethasone (prior randomisation or up to 1 day post randomisation)
- receipt of tociluzimab (prior randomisation or up to 1 day post randomisation)

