Every effort will be made to obtain follow-up data for all participants including those that stop treatment. The number and proportion of participants missing WHO COVID-19 status by treatment group and visit will be tabulated (see section 2.5 above). For participants who are discharged early the assumption will be made that they did not progress to grade 5 WHO scale. If there is a >5% rate of missing outcomes after this, we will impute missing WHO COVID-19 data in the primary analysis model using multiple imputation under the assumption of missing at random (MAR). That is the probability of being missing is not dependent on the values of unobserved data, conditional on the observed values of the variables included in the analysis model. Imputation under MAR using chained equations following the guidance of White et al. will be undertaken.⁴ Variables in the imputation model will include the variables in the primary analysis model described above plus baseline WHO COVID-19 score (3 or 4), age (<65 or ≥65), receipt of dexamethasone and/or tociluzimab at the time of or prior to randomisation into MATIS. Additional auxiliary variables that are suspected to be associated with the outcome and are predictors of missingness will also be included. These are receipt of any effective treatments post randomisation as a result of co-enrolment when occurring postrandomisation, and receipt of known effective treatments dexamethasone and tociluzimab postrandomisation (>1 day post randomisation) and WHO COVID-19 scores at day 1 and day 7. Using White et al.'s rule of thumb we will impute m datasets based on the percentage of participants with incomplete outcomes, where m will be rounded to the nearest 10, for example if 8% of participants have incomplete primary outcome then m=10 will be used.

Before undertaking the multiple imputation as described above we will impute any missing baseline data deterministically only using other baseline data, this includes the baseline WHO COVID-19 status, age, receipt of dexamethasone and/or tociluzimab at the time of or prior to randomisation into MATIS. To do this we will impute missing values with the mean values of observed data. In line with White et al., outcomes will be imputed separately for each treatment group.

Imputed datasets will then be analysed using the primary analysis model described above.

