The stage two primary analysis will consist of fitting one binomial regression model regardless of whether one or two experimental treatments progress from stage one. Specifically a generalized linear model with WHO COVID-19 status (<5 or \ge 5) as the outcome and treatment group, baseline WHO COVID-19 score (3 or 4), age (<65 or \ge 65), receipt of known effective treatments dexamethasone and/or tociluzimab, prior vaccination against COVID-19 (y/n) and receipt of paxlovid and/or molnupiravir at the time of or prior to randomisation into MATIS as covariates will be fitted. Effective treatments will be included as separate covariates in the primary analysis model. Given the anticipated small number of sites in this study, site will also be included in the model as a fixed effect. In the event that all participants are on one of the effective treatments that covariate will be removed from the model.

If including site as a fixed effect results in unstable model estimates e.g. if there are a number of sites with very few randomisations we will exclude site from the model and we will only adjust for baseline WHO COVID score, age group, receipt of known effective treatments dexamethasone and/or tociluzimab, prior vaccination against COVID-19, and receipt of paxlovid and/or molnupiravir.⁶ We will also consider not adjusting for paxlovid and/or molnupiravir if the number of participants receiving these are low. If after removing sites and treatments the model is not stable due to event rate:covariate ratio we will adjust for all covariates using a propensity score approach.

The model will be fitted with a binomial distribution and logit link function and the treatment effect will be reported as an odds ratio with corresponding 95% confidence interval and p-values. P-values will be one-sided and judged at the 0.027 level. Therefore, a two-sided p-value < 0.054 will be used to indicate a significant treatment effect.

The stage two model to be fitted to estimate the treatment effects will be:

$$logit(\pi_{ij}) = \beta_{0} + \beta_{1}RUX_{ij} + \beta_{2}FOS_{ij} + \beta_{3}WHO_{ij}^{0} + \beta_{4}AGE_{ij}^{0} + \beta_{5}DEX_{ij}^{0} + \beta_{6}TOC_{ij}^{0} + \beta_{7}VAC_{ij}^{0} + \beta_{8}PAX_{ij}^{0} + \beta_{9}MOL_{ij}^{0} + \beta_{10}SITE_{1} + \beta_{11}SITE_{2} + \cdots + \beta_{12}SITE_{i-1}$$

 RUX_{ij} : dummy variable for treatment ($RUX_{ij} = 0$ or 1) for participant i in jth site

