 FOS_{ij} : dummy variable for treatment ($FOS_{ij} = 0$ or 1) for participant i in jth site

 WHO_{ij}^0 : dummy variable for baseline WHO COVID-19 value for participant i in jth site (WHO_{ij})

0 or 1 where 0 indicates score of 3 and 1 indicates score of 4)

 AGE_{ij}^{0} : dummy variable for age-group ($AGE_{ij} = 0$ or 1 where 0 indicates <

65 years and 1 indicates \geq 65) for participant i

 DEX_{ij}^0 : dummy variable for receipt of dexamethasone at the time of or prior to randomisation (includes day of randomisation or one day post randomisation) ($DEX_{ij} = 0$ or 1) for participant i

 TOC_{ij}^0 : dummy variable for receipt of tociluzimab at the time of or prior to randomisation (includes

day of randomisation or one day post randomisation) ($TOC_{ij} = 0$ or 1) for participant i

 VAC_{ij}^0 : dummy variable for prior vaccination against COVID-19 at the time of or prior to randomisation (includes day of randomisation or one day post randomisation) ($VAC_{ij} = 0 \ or \ 1$) for participant i

 PAX_{ij}^0 : dummy variable for receipt of paxlovid at the time of or prior to randomisation (includes day of randomisation or one day post randomisation) ($PAX_{ij} = 0 \text{ or } 1$) for participant i

 MOL_{ij}^0 : dummy variable for receipt of molnupiravir at the time of or prior to randomisation (includes day of randomisation or one day post randomisation) ($MOL_{ij} = 0$ or 1) for participant i $Site_j$: dummy variable for each of the jth sites

 π_{ij} : probability of WHO COVID-19 \geq 5 for the ith participant in jth site

To account for missing outcomes in the primary analysis model we will impute missing WHO COVID-19 status using multiple imputation under the assumption of missing at random (MAR) as described in the primary statistical model at stage 1 section 3.1.2 plus the imputation model will contain the following additional variables: prior vaccination against COVID-19, and receipt of paxlovid and/or molnupiravir at the time of or prior to randomisation into MATIS, plus post-randomisation receipt of paxlovid and/or molnupiravir. Multiple imputation will be used for the final analysis regardless of levels of missingness at this stage.

As well as reporting odds ratios and 95% CIs, the model will be used to estimate the difference in proportion of participants with modified WHO COVID-19 Ordinal Score ≥ 5 .

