3.1.6 Stage 2 subgroup analysis for primary outcome

Subgroup analysis will be performed for the primary outcome for the final analysis only to explore the uniformity of the treatment effect. The following subgroups will be examined by adding a treatment-by-subgroup interaction term to the same analysis model as for the primary outcome:

- Sex: male vs female;
- Age: <65 years vs ≥65 years
- Obesity: $<25, 25-29.9, \ge 30$
- Chronic heart disease: yes vs no;
- Lung disease: yes vs no;
- Kidney disease: yes vs no;
- Liver disease: yes vs no;
- Diabetes: yes vs no;
- Immunocompromised: yes vs no;
- Smoking status: current vs non-smoker;
- CRP > 200mg/L: yes vs no and/or D-dimer >2500mg/mL: yes vs no;
- Time since onset of symptoms:0-5, 6-10, >10 days prior to randomisation

P-values for each interaction term will be presented. No adjustment for multiple tests will be made and the results will be viewed as hypothesis generating only. The consistency of estimates will be depicted visually by means of a forest plot.

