3.2.4 Length of stay

The time to discharge will be summarised by treatment arm using a Kaplan-Meier plot with extended at risk tables, detailing the numbers at risk, censored and discharged at each discrete time point, censoring at the day 28 visit. Withdrawals and deaths will be censored at the date of occurrence. In addition, summaries (means (SD) and median (IQR)) of length of stay will be tabulated amongst those that do not withdraw or die.

In addition, a Cox proportional hazards model will be used to estimate the hazard ratio of time to discharge between intervention arms with age (<65 or ≥65), site and receipt of known effective treatments dexamethasone and/or tociluzimab and vaccination status at the time of or prior to randomisation into MATIS included as covariates.

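### Drug starts up to one day after randomisation are adjusted for as baseline in the open-label primary model, so its odds ratio need not be the effect of allocation

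*SAP*

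**What the plan says.** The model text of SAP 3.1.3 lists the stage 2 covariates with no allowance for time after randomisation: "receipt of paxlovid and/or molnupiravir at the time of or prior to randomisation into MATIS as covariates will be fitted". The variable list below it defines the dexamethasone indicator as "receipt of dexamethasone at the time of or prior to randomisation (includes day of randomisation or one day post randomisation"), and gives tocilizumab, paxlovid, molnupiravir and vaccination the same window.

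The window recurs:

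- The stage 1 propensity score (SAP 3.1.2) has it for dexamethasone and, in the words "receipt of tociluzimab (prior randomisation or up to 1 day post randomisation"), for tocilizumab.
- SAP 3.1.5(i), 3.2.2 and 3.2.5 state it. Section 3.1.6 inherits it by adding an "interaction term to the same analysis model as for the primary outcome", and 3.2.1 and 3.2.3 reuse the 3.1.3 model.
- The imputation auxiliaries in 3.1.2 start where it ends: "receipt of known effective treatments dexamethasone and tociluzimab postrandomisation (>1 day post randomisation"). The mediation analysis in 3.1.5(ii) has the same cut-off.

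Other models use the timing phrase with no window, for example the Cox model in 3.2.4 ("vaccination status at the time of or prior to randomisation into MATIS included as covariates") and the blood measurements in 2.8.

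SAP 1.8 describes the efficacy population as "all randomised participants analysed in the treatment arm to which they were allocated to regardless of treatment subsequently received". SAP 1.2 says the trial is open label with treatment running from baseline, and 1.4.1 permits rescue before or after randomisation. Protocol 4.2 puts only baseline and stratification variables in the stage 2 model and sends later rescue and co-enrolment to supplementary analyses. The SAP is based on protocol v2.2 and the protocol supplied is v4.0, but the amendment log lists no change to the primary analysis in v3.0 or v4.0.

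**The concern.** A covariate measured before randomisation cannot be affected by allocation, so adjusting for it is safe. A drug started on day 0 after allocation, or on day 1, can be. Clinicians know the arm and may start dexamethasone or tocilizumab according to arm and early deterioration. Conditioning on such a start does two things. It removes any effect of allocation that acts through the early start. It also compares patients with different early courses across arms, because a start signals deterioration to a different degree in each arm. The resulting odds ratio need not be the total effect of allocation.

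The stage 2 odds ratio and its one-sided 0.027 test are the confirmatory result, and the plan has little that would show the problem. Because later receipt is counted only beyond one day, no listed analysis treats day 0-1 starts as post-randomisation. Section 3.1.5(ii) requires later treatment to precede the outcome; 3.1.3 sets no such order, so a start that follows a day 0-1 event could count as baseline. An unadjusted model is listed at stage 1 but not at stage 2. SAP 2.4 says only "Please see section 2.4 in SAP I. This will be undertaken for stage I and stage II", and SAP I is not among the documents, so whether its summaries show these starts by arm is unknown.

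**Working it through.** **Plan's figures.** With 5% missing, n1 = 57 × 0.95 = 54.15 and n2 = 152 × 0.95 = 144.4 per arm. The probability that Z1 exceeds z(0.75) and Z2 exceeds z(0.973), with correlation √(54.15/144.4) = 0.612 and risks of 50% and 30%, is 0.900 (unpooled) or 0.895 (pooled). The stated 90% reproduces. The family-wise error at 0.027 per arm is 0.0489. Neither figure is disputed.

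**Assumed inputs (none is in the documents, except that 50% is the plan's control rate).** Risk without the drug is 50%. On day 0-1, 30% of patients deteriorate, with relative risk (RR) 1.8 for the outcome. Starts among patients not already on the drug, if deteriorating / not deteriorating:

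- moderate gap: 70%/15% in one arm, 50%/10% in the other
- strong gap: 90%/20% in one arm, 40%/5% in the other

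RUX and FOS have no effect.

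**One case by hand: strong gap, 10% prior use, drug without effect, active arm starts more.**

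- Risk if not deteriorating: 0.5/(0.3 × 1.8 + 0.7) = 0.403. If deteriorating: 0.726.
- Active arm, new starts: 0.9 × (0.3 × 0.9 + 0.7 × 0.2) = 0.369. Counted as baseline users: 0.469, risk 0.591. The rest: 0.531, risk 0.420.
- SOC, new starts: 0.9 × (0.3 × 0.4 + 0.7 × 0.05) = 0.1395. Counted as users: 0.2395, risk 0.589. The rest: 0.7605, risk 0.472.
- OR among users: (0.591/0.409)/(0.589/0.411) = 1.01. OR among the rest: (0.420/0.580)/(0.472/0.528) = 0.81.
- The logistic model with arm and the indicator combines these to 0.87. Each arm's total risk is 50%, so the unadjusted OR is 1.00, and so is the OR adjusted for strictly prior use.

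**Large-sample fits.** With no gap, both definitions give OR 1.00. Ratio of the +1-day OR to the strict-baseline OR under the strong gap, over both directions:

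| Drug RR | 10% prior use | 30% | 80% |
|---|---|---|---|
| 1.0 | 0.87-1.15 | 0.93-1.08 | 0.99-1.01 |
| 0.9 | 0.92-1.09 | 0.97-1.04 | 1.00 |
| 0.8 | 0.97-1.03 | 0.99-1.00 | 0.99-1.01 |
| 0.7 | 0.97-1.03 | 0.95-1.05 | 0.98-1.02 |

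The moderate gap at 10% prior use gives 0.96-1.05 with no drug effect; at drug RR 0.8 it gives 0.99-1.01. The strict OR stays within 0.002 of the unadjusted OR in every scenario.

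**Stage 2 rejection at one-sided 0.027, no RUX/FOS effect.** Approximate check: with 144 per arm at 50% risk, SE(log OR) = √(2/(144 × 0.25)) = 0.236. For OR 0.87, ln(0.87)/0.236 = -0.59, and P(Z > 1.927 - 0.59) is about 9%. Simulation (three arms, two drugs, 10% prior use of the drug with the gap, 20,000 trials per scenario):

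| Scenario | Strict | +1-day |
|---|---|---|
| No drug effect, moderate gap | 2.6-2.8% | 1.7-4.2% |
| No drug effect, strong gap | 2.6-2.8% | 0.6-9.5% |
| Both drugs RR 0.8, strong gap | 1.1-6.1% | 0.9-7.5% |

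**Stage 1 pass rate at 0.25, no RUX/FOS or drug effect, 54 per arm, propensity score.** Strict about 25%. +1-day at 10% prior use: 21-28% (moderate), 16-36% (strong). At 80% prior use: 24-26%.

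**Two-stage power, 50% against 30%, no drug effect.** Strict about 89%. +1-day at 10% prior use: 87-92% (moderate), 77-94% (strong). At 80% prior use, strong gap: 88-90%. With drug RR 0.8, a strong gap, SOC starting more and 10% prior use: strict 75%, +1-day 70%.

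**Second model, built separately** (co-treatment OR 0.5-0.6, 20-50% prior users, an unmeasured severity factor, RUX/FOS effective). Strict OR to +1-day OR: equal starts 0.495 to 0.495; SOC 40% against active 20%, 0.519 to 0.508; 60% against 20%, 0.539 to 0.518; 70% against 20% with 20% prior users, 0.619 to 0.554.

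**The case against.** The window is disclosed and looks deliberate: the variable list can be read as defining the model text, and the later cut-offs dovetail with it. That is fair, but a deliberate choice can still put a post-allocation variable in the primary model.

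The largest figures assume a co-treatment that does nothing, while the SAP calls dexamethasone and tocilizumab effective. At drug RR 0.8 the two definitions nearly agree, and most of the departure from 2.7% rejection remains under the strict one. This stands as a limit on size. It does not make the window valid. Under the strong gap at 10% prior use, the +1-day OR stays near 0.87 or 1.15 at every drug RR from 1.0 to 0.7, so it recovers neither a direct effect of 1.00 nor, in general, the total effect. The strict OR (0.90 or 1.12 at RR 0.8) carries the total effect of allocation, including unequal background care, which is the ITT quantity.

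Thirty per cent deteriorating on day 0-1 is generous: protocol 1.3 gives about 30% over the whole admission, for the harder event of needing ventilatory support. With 10%, the strong-gap range for an inactive drug narrows to 0.945-1.06. Yet with an active drug (RR 0.7) the definitions still differ by about 6% at 10-30% prior use.

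Partial safeguards exist: event proportions by arm (SAP 2.7), from which a crude OR can be derived but no test is planned; the unadjusted model and non-binding rule at stage 1; removal of a drug that everyone receives; and the option to omit paxlovid and molnupiravir if few receive them. Patients are still analysed as randomised. What is at issue is what the adjusted OR estimates.

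**Conclusion.** The concern holds and should be fixed. The primary model, and the stage 1 propensity score, can condition on treatment started after allocation in an open-label trial, and no listed analysis would separate those starts out.

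The size is unknown, because it depends on day 0-1 start rates by arm that the documents do not give. Bias is nil without an arm gap, can go either way with one, and vanishes as prior use nears 100%. Under the assumed inputs the shift in the odds ratio runs from negligible to about 15%; the upper end needs low prior use, a strong gap, frequent early deterioration and an inactive drug. With an active drug, a few per cent is typical. Dexamethasone and tocilizumab matter most. Vaccination has the same wording but is immaterial in practice.

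**What to change.** Before unblinding:

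1. Reconcile the model text and variable list in SAP 3.1.3. There, in 3.1.2 and in the models that state or inherit the window (3.1.5, 3.1.6, 3.2.1 to 3.2.3, 3.2.5), define the four drug covariates as receipt documented before randomisation: by clock time, or by a date before the randomisation date where no time exists. Do not accept a same-day record as baseline merely because it was made at the baseline visit, since randomisation happens at that visit. Point 2.8, 3.2.4 and the baseline imputation covariates in 3.1.2 to the same definition.
2. Move the cut-offs for later receipt in 3.1.2 and 3.1.5(ii), and the co-enrolment window in 3.1.5(i), to match.
3. Make the stage 2 Standard of Care summary show day 0-1 starts of each drug by arm.
4. Keep the one-day window as a sensitivity analysis.

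The cost is wording and four re-derived indicators. Concomitant medications are scheduled at screening, baseline and day 1, and protocol 7.14 requires medication after enrolment to be recorded. No passage says clock times are recorded, hence the date rule; the existing cut-off at one day already needs dates. The downside is that some true same-day prior use is classed as not baseline, but the date rule does this independently of arm. With half of prior use so classed (30-80% prior use, drug RR 0.7-0.8, 144 per arm), null rejection stays at 2.6-2.9% and final-analysis power falls by at most 0.5 points, for example from 94.2% to 93.7%.
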